Individuals with past month use of cocaine, opioids, benzodiazepines, and methamphetamine or other illegal substances (other than marijuana) will be excluded. Individuals who report using marijuana greater than 15 days in the past 30 and/or alcohol greater than 25 days in the past 30 days will be excluded. Participants who choose not to answer questions related to inclusion/exclusion criteria will be excluded. Women will be excluded if they are breastfeeding or test positive for pregnancy (by urinalysis) at screening. Participants who weigh less than 110 pounds will also be excluded. Those who intend to quit tobacco/nicotine use in the next 30 days will be excluded and referred to cessation treatment.

In addition, participants who have previously participated in a study with exactly the same manipulations of ECIG type, setting, and liquid concentration will be excluded. Specifically, participants who have participated in HM20018290 will

not be eligible to participate in this protocol. Staff from this protocol will work with staff from HM20018290 (who are also listed on this protocol) to assure that there is no cross-participation between participants.

6. * Will individuals with limited English proficiency be included in or excluded from this research?

- Included
- Excluded - safety concerns if participants are unable to communicate with the study team
- Excluded - instruments/measures only validated in English
- Excluded - no prospect of direct benefit to individual participants**
- Excluded - minimal risk study
- Excluded - lack of budget/resources for translation and interpretation [provide an explanation in next question]
- Excluded - other reason [provide an explanation in next question]

7. Justify the inclusion and exclusion criteria if you are either targeting, or excluding, a particular segment of the population / community. Provide a description of the group/organization/community and provide a rationale.

N/A

Background, Rationale & Goals Section Complete

Protocol Progress:

- **INITIAL SETUP**
- **BACKGROUND, RATIONALE & GOALS**
- ③ RESEARCH PLAN
- ④ CONSENT PLAN
- ⑤ RISKS, PRIVACY & CONFIDENTIALITY
- ⑥ POPULATIONS WITH SPECIAL CONSIDERATIONS
- ⑦ INSTITUTIONAL REQUIREMENTS
- ⑧ DOCUMENTS

Click Continue below to go to the next section

Study Procedures

1. * Describe the study hypothesis and/or research questions. Use lay language whenever possible.

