Because there are no specific pre-in-person screening procedures for this study, all interested participants must go through the CSTP registry and agree to join that registry. All screening data collected from participants who choose to join the registry will be used in this study.

Participants who appear eligible will then be scheduled for an in-person screening visit (the in-person screening visit is part of this protocol, not part of the registry process). Upon arrival for the in-person screening visit, participants will be asked questions about possible COVID-19 symptoms/exposure. If answers to the questions are all "no", participants will be escorted to a session room, where they will provide informed consent if they choose to participate. The consent form will be read to participants either using a pre-recorded voice-over Power Point presentation, or in person by research staff, and participants will have the opportunity to ask questions to research staff via Zoom (for communication between the participant and staff from inside the session room to outside the session room) both during the presentation and afterwards. Signed consent will be obtained on a paper form. After consent, participants will be asked to complete other forms (see in-person screening forms: ICF, In-person screening survey). Participants will be asked for a urine sample that will be tested for cotinine (a metabolite of nicotine) and pregnancy (for participants who indicate their sex assigned at birth as female) and this information will be recorded on the Biochemical test/vitals form. Participants will also be able to view other questionnaires (document labeled "session measures"), via computer, and the study equipment. Study equipment includes the monitor for blood pressure and heart rate, as well as equipment for monitoring puffing behavior (a computer, tubing, and a mouthpiece that is attached to the ECIG when participants are using it). We may also take a photo (with no identifying information) of the participant's own brand cigarette pack, to aid in our efforts to purchase their own brand cigarettes.

Participants with blood pressure at the in person screening that is 140/90 or higher will be given information about blood pressure (see document).

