After screening and informed consent, eligible participants will enroll in this study, which is modeled on our previous work (e.g., Spindle et al., 2016; Hiler et al., 2017). A total of 32 participants are needed to complete the study. Once enrolled, participants will attend the lab for four additional experimental sessions (approximately 3 hours each) where they use an "open system" ECIG (Kanger Sub Box Mini and/or a Kangertech Sub Box Mini tank connected to hardware and/or software to limit puff duration) set to 30 watts, which will contain either 0mg, 6mg, 15 mg, or 30 mg nicotine-containing unflavored, unsweetened nicotine salt e-liquid. The design of this study is within-subjects, thus, all participants will complete four sessions that differ by the concentration of nicotine in the liquid. Sessions will be ordered by Latin-square. A Latin-square is a way of ordering conditions in a within-subjects study so that no condition follows another condition more than once within a given "square". This is different from random ordering but is preferred in studies with a small N.

The sessions will occur no more than 2 days per week and will be separated by at least 48 hours. The approximate total time that participants will be in the laboratory is 12.5 hours (30 minutes for screening and 12 hours for sessions). This does not include the 12 hours before each session that we ask participants to abstain from any nicotine/tobacco containing products.

During each session, participants will first complete a 10-puff product use period with the ECIG assigned for that session (2 second duration limit for each puff, using hardware and/or a computer program), then a 30-minute ad lib product use period, and then a cigarette/e-cigarette challenge paradigm. Sessions will be preceded by 12 hours tobacco/nicotine abstinence (to measure the extent to which each device/liquid combination suppresses nicotine/tobacco abstinence symptoms). In all sessions, participants will use topography-measurement equipment (a mouthpiece attached to the ECIG that is attached to a computer via tubing; the participant then puffs on the mouthpiece). Other outcomes include plasma nicotine, cardiovascular response (heart rate), and subjective effects (direct effects of the ECIG and nicotine, abstinence symptoms).

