1. * Select all of the types of samples that will be collected as part of this study.

- Amniotic Fluid
- Blood
- Buccal Smears
- Saliva
- Tissue
- Urine
- Stool
- Other

2. * Select all of the methods of blood collection that will be utilized in this study:

- Individual Needle Stick(s)
- Indwelling Catheter Placed Solely for This Study (note: study will be referred to full board for initial review)
- Indwelling Catheter Placed for Other Reason(s) (note: study will be referred to full board for initial review)
- Blood Collected at the Same Time as Non-Research Blood Collection(s)
- Other

3. * In order to collect urine, will an indwelling catheter be placed solely for the research study:

- Yes
- No

4. * Describe how the sample will be collected and the collection schedule. For each type of sample, include information about

- The procedures that will be followed to collect the sample
- The role(s) of the individuals who will collect the sample
- The volume/size range of the sample
- The timing and frequency of sample collection

Urine will be collected at the in-person screening to test for cotinine and pregnancy (pregnancy test for women only). Urine will not be stored for later use. Upon arrival at the CSTP for the research session, participants' breath CO will be measured to ensure compliance with the overnight abstinence criteria (i.e., CO less than or equal to half of the value at the in-person screening). Blood will be collected via intravenous catheter 5 times at each session (7ml each time), for a total of 20 samples per person in the entire study (140 ml in total). Blood will not be collected more than 2 times per week.

5. * Will genetic testing or genetic analyses be conducted on any of the samples:

- Yes
- No

Active Internet Data Collection

1. * Describe the platform/technology chosen for collecting the data and transmitting data securely over the internet. If proposing a non-VCU approved platform, give the rationale for selecting the technology instead of a VCU-approved platform.

The in-person screening questionnaires, questionnaires administered during sessions, and the follow-up survey will be administered via REDCap. All of the data will be stored in REDCap, and viewing will be restricted to those personnel associated with this protocol (listed under personnel).

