View Participant	Phone_e-mail_text scripts_3.30.2022 Communication changes accepted revised 5.4.2022.docx - Phone, email, and text scripts	0.22	5/4/2022 3:23 PM	[REDACTED]	Recruitment/Advertising	Yes

Pertinent Results and Incidental Findings

1. * Is it likely investigators could discover a participant's previously unknown condition (e.g. pregnancy, disease, suicidal thoughts, wrong paternity, genetic results, or other findings that may be of importance to health or well-being) or if a participant is engaging in illegal or reportable activities:

Yes
 No

2. * Describe what possible pertinent results or incidental findings stemming from research-only procedures may be discovered.

During screening, we assess blood pressure.

During screening, we assess if female participants are pregnant.

During screening, we ask questions about mar juana/cannabis use and other illicit drug use.

During screening and at the beginning of a session, we ask about respiratory and gastrointestinal symptoms.

3. * Explain what actions or procedures research personnel should take to inform the PI of such a discovery :

If a participant's blood pressure is high, research staff will advise the participant to talk to their own doctor and to get treatment. The "Information about Blood Pressure" sheet will be given to participants if their blood pressure is high, which lists a variety of community resources.

If a participant is pregnant, research staff will advise the participant to seek prenatal care.

If a participant reports mar juana/cannabis use, although this is an illegal activity, the research staff will not take any actions. This study has a certificate of confidentiality, which provides additional protections for participants.

Individuals who engage in illicit drug use in the past month will not be eligible for an in-person screen or to participate in the clinical laboratory portion of the study.

Answers given about respiratory and gastrointestinal symptoms will be compared to the participants' previous answers, and if any symptoms have increased, [name] will be asked to review the symptoms. In some cases, we may contact [name] to determine if a session can proceed.

4. * Will findings be disclosed to participants and/or any other person/group outside of the study team?

Yes
 No

5. * Describe a communication plan addressing:

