1. What criteria will be used to determine which pertinent and/or incidental findings will be communicated, including the following for health related findings:

--- The reliability of the tests/images, such as being done in a CLIA-certified lab,
--- Whether the meaning and significance of the findings are known,
--- Whether the findings reveal a significant risk of a serious health condition,
--- Whether there is an accepted treatment for the health condition revealed by the findings, and
--- The risks both of knowing and not knowing the findings, including risks to family members from genetic testing results.

2. What information will be provided during the consent process about the plans for communicating pertinent and/or incidental findings;

3. Whether the participants will be given the option of refusing communication of some or all types of pertinent and/or incidental findings to themselves, their family members, and/or any other individuals or groups; and

4. To whom and by whom the findings will be communicated, when, and how.

Findings for blood pressure and pregnancy will be communicated to participants verbally during the in-person screening visit. These findings will only be communicated to the participant and will be communicated by the study staff conducting the screening. In the event of high blood pressure or a positive pregnancy test, the study staff will communicate this information and advise the participant to seek treatment.

The reliability of the blood pressure monitor is not known, nor is the reliability of the pregnancy tests we use.

The blood pressure measurement could reveal a significant health risk, depending on how high it is.

There is accepted treatment for high blood pressure.

There are no risks to knowing or now knowing about high blood pressure or pregnancy.

Participants do not have the option of refusing communication about their blood pressure reading or pregnancy test results.

Any adverse events may be reported to the study sponsor at FDA/NIH as needed/per their request.

Any information about adverse events reported to individuals outside of the study team will not include participants' names, DOBs, or other identifying information. Currently, the consent form indicates that such data might be shared with the study sponsor:

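### Minor safety improvement: the pregnancy exclusion rests on one urine test at screening, while the four product-use sessions have no latest date; repeat the test when the last negative result is stale

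*Protocol*

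**What the plan says.** Every place in the protocol that describes the pregnancy test puts it at the in-person screening.

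- Study Population, question 5 (exclusion criteria): "Women will be excluded if they are breastfeeding or test positive for pregnancy (by urinalysis) at screening".
- Study Procedures, question 7 (screening visit): "Participants will be asked for a urine sample that will be tested for cotinine (a metabolite of nicotine) and pregnancy". The pregnancy test is for participants who report female sex assigned at birth.
- Sample Collection Details, question 4, lists urine collection for that visit only.
- Pertinent Results and Incidental Findings, question 2: "During screening, we assess if female participants are pregnant". Question 5 places the reporting at the same visit: "Findings for blood pressure and pregnancy will be communicated to participants verbally during the in-person screening visit". It also says: "The reliability of the blood pressure monitor is not known, nor is the reliability of the pregnancy tests we use".

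The session description and timeline (Study Procedures, question 7) list breath CO, blood pressure, heart rate, catheter, five blood samples, questionnaires and topography, but no urine sample. One check is repeated: "During screening and at the beginning of a session, we ask about respiratory and gastrointestinal symptoms".

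On timing, Study Procedures, question 7, states: "The sessions will occur no more than 2 days per week and will be separated by at least 48 hours". No longest interval is given from screening to session 1, between sessions, or to the last session. Risks, Discomforts, Potential Harms and Monitoring, question 5, allows rescheduling after failed abstinence with no set number of attempts, and lets catheter attempts run over several sessions.

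**The concern.** The exclusion is enforced on one day, but product is used on at least four later days that have no end date. Someone who becomes pregnant after screening, or whose pregnancy was too early to show then, can go through the remaining sessions with the protocol followed to the letter. The protocol itself relays advice that vaping products are unsafe in pregnancy (Risks section, questions 1 and 2). It also tells participants that the study liquids may be stronger than those they are used to. What is at stake is participant safety and the meaning of a stated exclusion. No estimate, test or power figure is affected.

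**Working it through.** The protocol gives no figure on this point to reproduce. The check is of dates and counts.

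**Inputs from the protocol:** 1 urine pregnancy test; 4 sessions (0, 6, 15 and 30 mg/ml); at least 48 hours between sessions; at most 2 session days per week; 32 completers; up to 75 consented. **Assumed:** screening the day before session 1 (day -1). No sex split or pregnancy rate is given.

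**Fastest schedules the spacing rules allow, session 1 = day 0**

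| Reading of the weekly limit | Session days | Age of screening test at sessions 1 to 4 |
|---|---|---|
| Calendar week | 0, 2, 4, 6 | 1, 3, 5, 7 days |
| Any 7 days | 0, 2, 7, 9 | 1, 3, 8, 10 days |

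The slowest schedule has no bound.

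**Retests under a rule of retesting when the last negative is more than 7 days old**

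- Calendar-week schedule: the oldest age is 7 days, which is not more than 7, so 0 retests.
- Any-7-days schedule: session 3 falls at 8 days, so 1 retest. Session 4 is then 2 days after that negative, so no more.
- Slow schedules: if every gap, including screening to session 1, is more than 7 days, there is a retest at each session, so 4.

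**Ceiling on the number of tests (slow schedule throughout)**

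- Completers, if all were female: 32 x 4 = 128.
- Non-completers, if all 75 - 32 = 43 passed screening, were female and attended three sessions: 43 x 3 = 129. Total 257.
- Female share assumed 25%: 8 x 4 + 10.75 x 3 = about 64. Assumed 75%: 24 x 4 + 32.25 x 3 = about 193.

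On the fastest schedules the same participants need between 0 and 75 x 1 = 75 retests if all were female, or at most about 19 to 56 at a 25% to 75% share. Repeated sessions can add tests on either basis, and their number is not capped.

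**How often it might matter (illustration only).** Assume 16 women and an annual pregnancy rate r of 2% to 10%. The chance of at least one pregnancy starting within w weeks of screening is 1 - (1 - r)^(16w/52).

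| Weeks from screening to last session | r = 2% | r = 10% |
|---|---|---|
| 2 | 1.2% | 6.3% |
| 4 | 2.5% | 12.2% |
| 12 | 7.2% | 32.2% |

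These values rest wholly on the assumed number of women and rate. They show that elapsed time drives the risk, which is why a rule tied to the age of the last test suits it.

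**The case against.** The strongest reply is that nothing here is wrong or contradictory. The protocol states a screening-time criterion and keeps to it throughout; it describes no recheck of cotinine, weight or drug use either. The added harm is small. Every participant smokes at least 5 cigarettes a day, vapes daily, or is a dual user. Each session follows 12 hours of abstinence and has 10 puffs, 30 minutes of ad lib use and 5 minutes with the participant's own product. The Risks section, question 2, holds that study exposure does not exceed ordinary life. All of this stands as a limit on severity. One qualification: the example used there is a smoker of at least 8 cigarettes a day, whereas the inclusion criteria admit 5.

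A reader might infer more than the text supports:

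- **That open-ended rescheduling increases exposure.** A visit that fails the abstinence check lengthens the time since the test but adds no product use. Only a session repeated after an equipment fault (Compensation section) could add some.
- **That the pregnancy tests are poor and a retest cures false negatives.** The protocol says their reliability is not known, not that it is low, and a repeat of the same test shares that uncertainty. The case rests on elapsed time.
- **That a known pregnancy could not be acted on.** The Risks section, question 5, already lets the investigator or nurse withdraw a participant for any safety concern.
- **That participants are never asked about pregnancy again.** The session measures, consent form and monitoring plan are not shown and may include such a question. It would still miss an unknown or undisclosed pregnancy.
- **That a test is needed at every session.** Sessions can be 48 hours apart, and nothing in the protocol makes a test that often useful.

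**Conclusion.** The point holds as a minor, low-cost safety improvement. The text is consistent in placing the only described urine pregnancy test at screening and sets no latest session date, so an unknown or undisclosed pregnancy that begins or becomes detectable later would not be found by testing. At session 4 the result is at least 7 or 10 days old if screening is the day before session 1, and older if screening is earlier. The number of participants affected cannot be derived from the protocol and is probably small with 32 completers. A reading that the protocol contradicts itself, or that the study exposes participants to materially more nicotine than usual, is not supported. Low cost is a judgement: the protocol gives no prices, but the test is non-invasive and already in use.

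**What to change.** 1. In the session procedures (Study Procedures, question 7) and in Sample Collection Details, question 4, add a repeat urine pregnancy test for participants tested at screening whenever the last negative is older than a stated short interval, for example 7 days. Do it in the existing one-hour waiting period, after abstinence is confirmed and before product use. State that the session does not proceed if the test is positive.
2. Add a pregnancy and breastfeeding question to the pre-session symptom check, unless the session measures already contain one.

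The cost is the small number of tests worked out above, no added session time in principle, and an occasional withdrawal and replacement. A visit that fails the abstinence check uses no test. Testing at every session whatever the interval, and listing pregnancy as a separate withdrawal ground, are not needed.

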Please note that beginning July 1, 2020, per Chapter 524 of the 2020 Acts of Assembly, which the Governor signed on March 31, 2020, Virginia law now permits us to recruit individuals aged 18-55. This law "Provides an exception to the law prohibiting possession of tobacco products, nicotine vapor products, or alternative nicotine products by a person less than 21 years of age when such possession is part of a scientific study being conducted by an organization for the purpose of medical research to further efforts in cigarette and tobacco use prevention and cessation and tobacco product regulation, provided that such medical research has been approved by an institutional review board pursuant to applicable federal regulations or by a research review committee."

5. * List the study exclusion criteria:

Individuals with the following self-reported current, diagnosed medical condition(s) will be excluded automatically: uncontrolled high blood pressure above 160/100 (via self-report or observed at screening), heart-related conditions (e.g., recent heart attack/stroke, coronary heart disease), severe immune system disorders (e.g., HIV/AIDS, multiple sclerosis), respiratory disorders (e.g., COPD, asthma), kidney diseases, liver diseases (e.g., cirrhosis), or seizures.

Individuals with other self-reported current, diagnosed medical conditions (e.g., diabetes, thyroid disease, lyme disease) will be considered for exclusion after consultation with the PI and medical monitor. We ask a variety of questions about participants' medical conditions that are not necessarily exclusionary in order to be able to consult with the medical monitor about these conditions. Participants with any medical condition/medication that may affect participant safety, study outcomes, or biomarker data will be excluded based on these consultations.

Participants with self-reported current, diagnosed psychiatric conditions, and who are currently under the care of a physician for psychiatric conditions, or who report current psychiatric treatment or psychotropic medication use will be excluded.

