This protocol uses established methods and procedures and involves only minimal risk to participants. Twelve hours of tobacco/nicotine abstinence may cause mild discomfort and nicotine abstinence symptoms. Nicotine abstinence symptoms are not medically dangerous but participants may experience include; irritability, anxiety and restlessness, excessive hunger, difficulty concentrating, and sleep disturbance. The risks of using ECIGs/nicotine are routine for the target population. Risks of nicotine use include sweating, lightheadedness, dizziness, nausea, and nervousness. These effects are unlikely in individuals who use tobacco products regularly. In addition, some people who use e-cigarettes have experienced seizures (<https://www.fda.gov/tobacco-products/ctp-newsroom/some-e-cigarette-users-are-having-seizures-most-reports-involving-youth-and-young-adults>). These have been reported among individuals with a history of seizures as well as among individuals using other substances such as marijuana and amphetamines, as well as among others. In addition, recently there have been some cases of e-cigarette use being associated with respiratory illnesses such as difficulties breathing, cough, shortness of breath and/or chest pain before hospitalization. In some cases, e-cigarette use has led to death, although most of these cases have been related to vaping THC. In some cases symptoms of mild to moderate gastrointestinal illness such as nausea, abdominal pain, vomiting, diarrhea, or fevers or fatigue have been reported. The Centers for Disease Control and Prevention advises that e-cigarette, or vaping products are unsafe for youths, young adults, or women who are pregnant. Please note that we recruit cigarette smokers who are aged 18 or older but consider recruitment of individuals 18 -25 as minimal risk, as the definition of "minimal risk" includes: "...the probability and magnitude of harm or discomfort anticipated in the research are not greater in and of themselves than those ordinarily encountered in daily life or during the performance of routine physical or psychological examinations or tests." Our inclusion criteria make clear that participants in this study are exposed to nicotine in their daily life, thus the risk of this exposure are, by definition, minimal. Adults who do not currently use tobacco products should not start using e-cigarette, or vaping, products.

Blood sampling involves the minor risk of infection and bruising at the catheter site.

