Participant safety and rights will be protected by highly trained staff that is well-versed in the importance of maintaining confidentiality. Participants will be informed of the potential symptoms of nicotine abstinence/withdrawal, and will be told that they are free to leave the study at any time. Risk of infection from blood sampling is minimized by trained nursing staff, disposable equipment, and aseptic nursing procedures. In the 15 plus years of operation, the CSTP has completed numerous IRB-approved studies without participant injury or a breach of confidentiality.

In addition, non-invasive computerized monitoring equipment allows for minute-by-minute, real time monitoring of participants' heart rate. If needed, we can monitor blood pressure as well throughout the session. Research personnel are trained to alert the research nurse if heart rate continually exceeds 120 beats per minute, if systolic BP continually exceeds 160 mm Hg, or if diastolic BP continually exceeds 100 mm Hg. Individuals whose heart rate and/or BP levels remain elevated will be monitored by the nurse, and if necessary emergency responders will be notified. Emergency medical coverage is available via the emergency room that is approximately 1.5 miles from the CSTP.

In the case of nicotine abstinence symptoms, the project products will possibly alleviate these risks. Participants will be provided with water at all times.

The risk of seizures is minimized by excluding participants with any history of seizures, and by having a full-time RN available, as well as monitoring of vital signs. In addition, some of the reported seizures occurred in users who were using other substances such as marijuana or amphetamines--the risk of seizures in this study is reduced as we are administering nicotine and no other substances.

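### The eligibility rule for seizures can be read more narrowly than the exclusion of any seizure history that the risk section gives as a safeguard

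*Protocol*

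**What the plan says.** Two parts of the protocol bear on who is kept out because of seizures.

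- **Risks, Discomforts, Potential Harms and Monitoring, item 2** describes how the risk is reduced: "The risk of seizures is minimized by excluding participants with any history of seizures". It adds other protections: "by having a full-time RN available, as well as monitoring of vital signs", and the fact that the study administers only nicotine.
- **Study Population, item 5** gives the exclusion criteria. The automatic medical exclusions open with "Individuals with the following self-reported current, diagnosed medical condition(s) will be excluded automatically", and the list closes with "kidney diseases, liver diseases (e.g., cirrhosis), or seizures". A second group is sent for consultation with the PI and medical monitor: "Individuals with other self-reported current, diagnosed medical conditions". A catch-all follows: "Participants with any medical condition/medication that may affect participant safety, study outcomes, or biomarker data will be excluded based on these consultations". The psychiatric exclusion opens in the same way: "Participants with self-reported current, diagnosed psychiatric conditions".

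Item 1 of the risk section explains why seizure history matters. Of seizures in e-cigarette users it says: "These have been reported among individuals with a history of seizures", while noting that they also occurred in others.

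**The concern.** The safeguard described to the IRB covers a whole lifetime. The criterion that staff would apply sits under a heading that speaks of conditions that are current and diagnosed. Someone with one seizure years ago, or a seizure never worked up, may have no current diagnosis to report. Taken literally, the criterion lets that person through to sessions with liquid of up to 30 mg/ml nicotine at 30 W, although the risk section says such people are excluded.

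What is at stake is protection of a group that the protocol itself singles out. Of the seizure protections listed, the exclusion is the only one that keeps these people out of the study. The nurse and the monitoring act after enrolment. The assurance that nothing but nicotine is given concerns what the study supplies.

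**Working it through.** No arithmetic applies, and the plan states no figure to reproduce. The check is a comparison of texts.

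**1. Scope of each statement, read literally.**

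| Case | Risk section, item 2 | Automatic list, Study Population, item 5 |
|---|---|---|
| Current, diagnosed seizure disorder | Excluded | Excluded |
| Past, resolved seizure | Excluded | Not clearly excluded |
| Seizure never diagnosed | Excluded | Not clearly excluded |

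**2. Does the rest of the eligibility text close the gap?** In Study Population, items 4 and 5, the limit to current, diagnosed conditions appears three times: in the automatic list, the consultation route and the psychiatric exclusion. The word 'history' does not appear. The catch-all does not repeat the limit and could remove some people with a past seizure. But it works through consultations introduced for conditions that are themselves current and diagnosed, and the outcome is decided case by case. That is not a blanket exclusion. The inclusion criterion of being healthy by self-report does not mention seizures either.

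**3. Does the limit really govern every entry in the list?** No. Two entries do not fit it. High blood pressure may be established by a reading at screening, which need be neither self-reported nor diagnosed. A recent heart attack or stroke is a past event. The opening is therefore loosely drafted, and seizures, which are events and carry no time limit of their own, could be meant to include past ones. On the other hand, the heart attack and stroke entry carries its own time word, and the seizure entry has none to show that past events count.

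**4. Can the risk section be relied on to settle the meaning?** Not safely. Elsewhere it departs from the eligibility section. It says cigarette smokers must report at least 8 cigarettes per day and have a screening CO of at least 7 ppm. Study Population, item 4, asks for at least 5 per day and sets no CO threshold for entry.

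The result is that the criterion has a narrow and a broad reading, and only the broad one delivers the stated safeguard.

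**The case against.** The strongest reply is that both texts are answers in one IRB form, with no separate protocol document and nothing that ranks one above the other. The statement in the risk section is then itself a written commitment, and it tells staff what seizures means in the list. Since the list already contains entries that break the limit to current, diagnosed conditions, applying that limit strictly to seizures alone is selective. Both statements can be true together, unlike two conflicting numbers.

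Much of this stands. A reader might infer a flat contradiction, and the documents do not support that, because an ordinary reading brings the two texts into agreement. A reader might also infer that people with a past seizure have been or will be enrolled. That is not supported either: the registry and in-person screening questions decide what is asked in practice, and they are not shown. The nurse, the vital-sign monitoring and the absence of other administered substances hold whichever reading is used.

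What the reply does not remove is that the criterion leaves the choice of reading to whoever applies it, and that the catch-all leaves exclusion to judgement.

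**Conclusion.** The point holds as a minor participant-safety ambiguity. The eligibility rule can be read as not excluding a past, resolved or undiagnosed seizure, so as written it does not guarantee the exclusion that the risk section claims.

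Its size cannot be given in numbers, because the protocol reports no count of screened people with a past seizure. Sample size, power and analysis are untouched. The conclusion rests on the protocol text alone and assumes that staff may work from the exclusion list without consulting the risk section. If the screening forms already ask about any past seizure and staff exclude on the answer, the gap is one of wording only.

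**What to change.** In Study Population, item 5, take seizures out of the list of current, diagnosed conditions and add a separate automatic exclusion, for example: *any history of seizures (current or past, by self-report)*. This matches the risk section, item 2, which then needs no change. Check that the registry and in-person screening questions ask about past as well as current seizures.

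The cost is a one-line amendment and at most a slightly smaller eligible pool. If practice already follows the risk section, conduct does not change.
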